### **5.6. Investigational Product Storage**

The investigator or an approved representative, eg, pharmacist, will ensure that all investigational products, including any comparator and/or marketed products, are stored in a secured area with controlled access under required storage conditions and in accordance with applicable regulatory requirements.

Investigational products should be stored in their original containers and in accordance with the labels.

Any storage conditions stated in the SRSD (IB for PF-04449913 and EU SPC for Vidaza®, EU SPC for Cytarabine, and EU SPC for Daunorubicin) will be superseded by the storage conditions stated on the product label.

Site systems must be capable of measuring and documenting (for example, via a log), at a minimum, daily minimum and maximum temperatures for all site storage locations (as applicable, including frozen, refrigerated, and/or room-temperature products). This should be captured from the time of investigational product receipt throughout the study. Even for continuous-monitoring systems, a log or site procedure that ensures active evaluation for excursions should be available. The intent is to ensure that the minimum and maximum temperature is checked each business day to confirm that no excursion occurred since the last evaluation and to provide the site with the capability to store or view the minimum/maximum temperature for all non-working days upon return to normal operations. The operation of the temperature monitoring device and storage unit (for example, refrigerator), as applicable, should be regularly inspected to ensure they are maintained in working order.

Any excursions from the product label storage conditions should be reported to Pfizer upon discovery. The site should actively pursue options for returning the product to the storage conditions described in the labeling, as soon as possible. Deviations from the storage requirements, including any actions taken, must be documented and reported to Pfizer.

Once an excursion is identified, the investigational product must be quarantined and not used until Pfizer provides permission to use the investigational product. It will not be considered a protocol deviation if Pfizer approves the use of the investigational product after the temperature excursion. Use of the investigational product prior to Pfizer approval will be considered a protocol deviation. Specific details regarding information the site should report for each excursion will be provided to the site.

Receipt of materials, door opening and closing, and other routine handling operations where the products are briefly out of the temperature range described in the labeling are not considered excursions.

Site staff will instruct subjects on the proper storage requirements for take home investigational products and how to report excursions.

### **5.7. Investigational Product Accountability**

The investigative site must maintain adequate records documenting the receipt, use, loss, or other disposition of the investigational product supplies. All investigational products will be accounted for using a drug accountability form/record. At each dispensing visit (Cycle 2 Day 1, Cycle 3 Day 1, Induction 1, Induction 2, etc. or when there is a dose reduction), all unused or partially used bottles of glasdegib/placebo must be returned by patients to the Investigator. The number of tablets returned by the patient at the end of the cycle (or induction 1, 2) will be counted, documented and recorded.

#### **5.7.1. Destruction of Investigational Product Supplies**

The sponsor or designee will provide guidance on the destruction of unused investigational product (eg, at the site). If destruction is authorized to take place at the investigator site, the investigator must ensure that the materials are destroyed in compliance with applicable environmental regulations, institutional policy, and any special instructions provided by Pfizer, and all destruction must be adequately documented.

### **5.8. Concomitant Treatment(s)**

All concomitant medications and treatments must be recorded in the CRF except during the HSCT period from the first day of conditioning until a subject resumes glasdegib or placebo post HSCT. During this HSCT period, no concomitant medications (other than transplant conditioning regimen) will be collected. If a patient resumes glasdegib or placebo following HSCT, HSCT-related Medical History must be provided. This will include information regarding ongoing medical conditions and their associated concomitant medications that started from the first day of conditioning until the time of re-starting glasdegib or placebo therapy.

Any prior treatment received within 28 days prior to study entry (including hematopoietic growth factor receptor agonists: erythropoietin, granulocyte colony stimulating factor (G-CSF), romiplostim, eltrombopag) will be recorded in the CRF.

In addition, any transfusion (red blood cells or platelets) within 8 weeks prior to randomization should be recorded in the CRF for the non-intensive study only. Transfusions (red blood cells or platelets) will not be recorded during the HSCT period unless part of ongoing Medical History once they resume glasdegib/placebo.

All prior therapies used to treat AML will be recorded regardless of when they were received by the subject. Information collected will include dates of use, best treatment response and the reasons for stopping therapy.

Every concomitant treatment, blood products, growth factors, as well as interventions, required by the subjects during the active study treatment (and up to 28 days following last study drug administration or until initiation of another anti-cancer treatment) and the reason for its administration must be recorded on the CRF.

### **5.8.1. Restricted or Prohibited Concomitant Medications**

The following medications are not allowed during the active study treatment period:

- Agents used to treat AML;
- Investigational agents;
- Concurrent administration of herbal preparations;
- CYP3A4/5 Inducers: A drug-drug interaction study in health subjects with the strong CYP3A4 inducer, rifampin, resulted in a 70% decrease in plasma exposures ( $AUC_{inf}$ ) and a 35% decrease in peak plasma concentration ( $C_{max}$ ) of a single 100-mg oral dose of glasdegib. Therefore co-administration of glasdegib and moderate/strong CYP3A4/5 inducers is not permitted. A comprehensive list of moderate/strong CYP3A4/5 inducers is provided in [Appendix 5](#). However, if you are uncertain whether a concomitant medication is contraindicated, you should contact the Sponsor study team.

The following medications have use restrictions during the active study treatment period:

- CYP3A4/5 Inhibitors: In a healthy volunteer study, ketoconazole, a potent CYP3A4/5 inhibitor, produced a 2.4-fold increase in plasma exposure and a 1.4-fold increase in peak plasma concentration of glasdegib. Therefore a potential exists for drug-drug interactions with CYP3A4/5 inhibitors, and co-administration of glasdegib/placebo in combination with moderate/strong CYP3A4/5 inhibitors is not recommended. Selection of concomitant medication with no or minimal CYP3A4/5 inhibition potential is recommended. Moderate/strong CYP3A4/5 inhibitors ([Appendix 6](#) and [Appendix 7](#)) should be used with caution and only if considered medically necessary. If a moderate/strong CYP3A4/5 inhibitor is to be initiated in addition to glasdegib/placebo, the guidance provided in [Section 7.1.7](#) and dose modifications for QT prolongation per [Table 10](#) must be followed. If you

are uncertain whether a concomitant medication is a CYP3A4 inhibitor, you should contact the Sponsor study team.

- Drugs with a known risk of Torsade de pointes (TdP): Glasdegib has been shown to have the potential to prolong the QTc interval in pre-clinical studies. In the first-in-subject study as single agent, Grade 3 QTcF prolongation was observed at the highest doses tested (400 mg and 600 mg). While the glasdegib dose evaluated in this study is 100 mg, the concomitant administration of glasdegib and drugs with a known risk of Torsade de pointes should be avoided whenever possible. A list of such drugs is provided in [Appendix 8](#). Use of these drugs is not recommended unless there are no alternatives. If a TdP drug is to be initiated in addition to glasdegib/placebo the guidance provided in [Section 7.1.7](#) and dose modifications for QT prolongation per [Table 10](#) must be followed.
- QT prolonging medications (without a risk of TdP) should be avoided whenever possible.
- Concomitant administration of multiple moderate/strong CYP3A4/5 inhibitors, TdP drugs, and/or QT prolonging medications (without a risk of TdP) is not recommended.

## **5.8.2. Permitted Concomitant Medications**

### **5.8.2.1. Best Supportive Therapy**

Best Supportive Therapy (BST) administration is permitted and encouraged according to Institutional guidelines for all subjects on study. BST will be provided by the site and may vary depending on the subject's signs and symptoms, site current practice, and country practice. It includes medications and supportive measures that may palliate disease-related symptoms, improve quality of life, prevent and treat bacterial, fungal or viral infections. BST may include:

- Blood transfusions;
- Platelet transfusions;
- Prophylactic antimicrobials (recommended particularly for intensive chemotherapy arm according to institutional guidelines);
- Antibiotics ([Section 5.8.1](#));
- Anti-fungal agents ([Section 5.8.1](#));
- Anti-viral agents ([Section 5.8.1](#)).

### **5.8.2.2. Hematopoietic Growth Factors**

Hematopoietic growth factors may be used per local standard of care and per local labels.

### **5.8.2.3. Anti-Emetic and Anti-Diarrheal Therapy**

Subjects should be pre-medicated with anti-emetics for nausea and vomiting before each dose of chemotherapy according to local practice and guidelines.

Primary prophylaxis of diarrhea is permitted at the Investigator's discretion. The choice of the prophylactic drug is up to the investigator.

### **5.8.2.4. Prophylactic Intrathecal Chemotherapy**

Prophylactic intrathecal chemotherapy is allowed, per investigator discretion.

### **5.8.2.5. Corticosteroids**

Chronic and acute administration of systemic and non-systemic corticosteroids (topical applications, inhaled sprays, eye drops or local injections) is allowed.

### **5.8.2.6. Surgery**

Caution is advised for any surgical procedures during the study. The appropriate interval of time between surgery and glasdegib required to minimize the risk of wound healing and bleeding has not been determined. Stopping glasdegib is recommended at least 7 days prior to surgery. Post-operatively, the decision to reinstate glasdegib treatment is up to the Investigator with Sponsor approval and should be based on a clinical assessment of satisfactory wound healing and recovery from surgery.

## **6. STUDY PROCEDURES**

### **6.1. Screening**

Screening can be accomplished over one or multiple visits over a 4-week period (28 days), unless specifically noted otherwise (ie, bone marrow sample collection). Protocol specific tests or procedures not considered standard of care can only be done after the subject has signed the Informed Consent document. The Informed Consent document may be signed up to 60 days prior to study entry.

See the [Schedule of Activities](#) for a complete list of assessments and procedures to be collected during the screening period.

### **6.2. Treatment Period**

See the [Schedule of Activities](#) for a detailed list of the assessments and procedures to be collected. Study entry is defined as when the subject is randomized into the IRT system. Subjects must be randomized into the IRT system prior to receiving first dose of study drug.

All assessments on Day 1 of each cycle should be collected pre-dose, unless documented otherwise.

CCI

In cases of unacceptable toxicity or pregnancy, the subject must be withdrawn from study drugs, have an end of treatment visit ([Section 6.3](#)), and be entered into the post-treatment follow-up phase ([Section 6.4](#)).

Subjects who permanently discontinue both study drugs (azacitidine or daunorubicin and cytarabine or glasdegib/placebo) for any reason (except death, or withdrawal of subject consent for follow-up) will enter into the follow-up phase of the study.

### **6.3. End of Treatment Visit**

The End of Treatment Visit should be scheduled as soon as possible once a patient has been withdrawn from study drug. For a detailed list of assessments and procedures to be completed please refer to the [Schedule of Activities](#).

Patients continuing to experience toxicity following discontinuation of treatment will be followed by the Investigator at least every 4 weeks until resolution or determination, in the Clinical judgment of the investigator, that no further improvement is expected.

### **6.4. Follow-up**

Follow-up contact will be completed at least 28 calendar days, and up to 35 calendar days after the last administration of the investigational product to capture any potential adverse events (see the [Time Period for Collecting AE/SAE Information](#) section) and to confirm appropriate contraception usage (see the [Contraception](#) section). Contact with the subject may be done via a phone call.

Please refer to the [Schedule of Activities](#) for details on assessments to be completed during the 2 types of follow-up visits: post treatment follow-up visits (first 2 years following last dose of study medication) and long-term follow-up ( $\geq 3$  years).

Subjects will be followed for survival for up to 5 years from the first visit of the last subject randomized in the study, or until death, or consent withdrawal. Public records may be used for contact information and/or to document date of death, as permitted by local law.

### **6.5. Subject Withdrawal**

Subjects may withdraw from the study at any time at their own request, or they may be withdrawn at any time at the discretion of the investigator or sponsor for safety (see also the [Withdrawal from the Study Due to Adverse Events \(see also the Subject Withdrawal Section\)](#) section) or behavioral reasons, or the inability of the subject to comply with the protocol-required schedule of study visits or procedures at a given study site.

Reasons for withdrawal of study treatment may include:

- Objective disease progression in the Intensive and Non-Intensive Chemotherapy Study or Treatment Failure or Hematologic relapse (Lack of Efficacy) in the Intensive Chemotherapy Study according to the 2017 ELN Recommendations ([Appendix 4](#)):
- Global deterioration of health status requiring discontinuation;

- Unacceptable toxicity (of either study treatment);
- Pregnancy;
- Significant protocol violation;
- Lost to follow-up;
- Subject refused further treatment;
- Study terminated by sponsor;
- Death.

Reasons for withdrawal from study follow-up may include:

- Study terminated by Sponsor;
- Lost to follow-up;
- Withdrawal of subject consent for any further contact;
- Death.

If a subject does not return for a scheduled visit, every effort should be made to contact the subject. All attempts to contact the subject and information received during contact attempts must be documented in the subject's medical record. In any circumstance, every effort should be made to document subject outcome, if possible. The Investigator should inquire about the reason for withdrawal, request that the subject return all unused investigational product(s), request that the subject return for a final visit, if applicable, and follow up with the subject regarding any unresolved AEs.

If the subject withdraws from the study, and also withdraws consent for disclosure of future information, no further evaluations should be performed, and no additional data should be collected. The sponsor may retain and continue to use any data collected before such withdrawal of consent.

**Withdrawal of consent:**

Subjects who request to discontinue receipt of study treatment will remain in the study and must continue to be followed for protocol specified follow-up procedures. The only exception to this is when a subject specifically withdraws consent for any further contact with him or her or persons previously authorized by the subject to provide this information. Subjects should notify the investigator in writing of the decision to withdraw consent from future follow-up, whenever possible. The withdrawal of consent should be explained in detail in the medical records by the investigator, as to whether the withdrawal is only from further receipt of investigational product or also from study procedures and/or post-treatment study follow-up, and entered on the appropriate CRF page. In the event that vital status

(whether the subject is alive or dead) is being measured, publicly available information should be used to determine vital status only as appropriately directed in accordance with local law.

### **Lost to follow-up:**

All reasonable efforts must be made to locate subjects to determine and report their ongoing status. This includes follow-up with persons authorized by the subject as noted above. Lost to follow-up is defined by the inability to reach the subject after a minimum of 2 documented phone calls, faxes, or e-mails. All attempts should be documented in the subject's medical records. If it is determined that the subject has died, the site will use locally permissible methods to obtain the date and cause of death. If, after all attempts, the subject remains lost to follow-up, then the last-known-alive date as determined by the investigator should be reported and documented in the subject's medical records.

## **7. ASSESSMENTS**

Every effort should be made to ensure that the protocol-required tests and procedures are completed as described. However, it is anticipated that from time to time there may be circumstances outside of the control of the investigator that may make it unfeasible to perform the test. In these cases the investigator will take all steps necessary to ensure the safety and well-being of the subject. When a protocol-required test cannot be performed, the investigator will document the reason for this and any corrective and preventive actions that he or she has taken to ensure that normal processes are adhered to as soon as possible. The study team will be informed of these incidents in a timely manner.

For samples being collected and shipped, detailed collection, processing, storage, and shipment instructions and contact information will be provided to the investigator site prior to initiation of the study.

### **7.1. Safety Assessments**

Safety assessments will include collection of AEs, SAEs, vital signs, physical examinations, triplicate ECGs (12-lead), laboratory assessments (including genetics), transfusions, HSCT-related information, and verification of concurrent medications and interventions.

#### **7.1.1. Cardiac Testing (MUGA/ECHO)**

For subjects to be enrolled in the Intensive Study, an ECHO or MUGA scan is required at screening. If the LVEF is  $\geq 50\%$ , the subject may proceed to their first induction therapy. If the LVEF is  $< 50\%$ , the subject may not be included in the Intensive Chemotherapy Study, per [Section 4.2](#) and may be eligible for the treatment in the Non-intensive Chemotherapy Study.

If a second cycle of induction chemotherapy is indicated, a second MUGA or ECHO is required prior to initiating the second cycle if clinically indicated (eg, subject exhibiting signs of cardiac failure). If the second MUGA or ECHO demonstrates a LVEF  $< 45\%$ , the subject is not eligible to receive additional induction chemotherapy and will be removed from the trial.

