12. **Echocardiogram (ECHO) or Multigated Acquisition Scan (MUGA):** Should be repeated before Induction 2 if signs of cardiac toxicity are observed and as clinically indicated thereafter. See [Section 7.1.1](#).
13. **Subject Registration:** Subject registration and assignment of treatment will be obtained from the centralized Interactive Response Technology (IRT).
14. **Glasdegib or Placebo Dosing:** Treatment will be administered in 28-day cycles. Glasdegib or placebo will be administered orally once daily, continuously, preferably in the morning at approximately the same time each day. Where possible, glasdegib will be administered together with daunorubicin IV injection during induction. Patients may continue on glasdegib treatment for up to a maximum of 2 years, as long as they demonstrate clinical benefit and do not have CR MRD-negative disease post consolidation/HSCT as confirmed at 2 consecutive time points.
15. **Daunorubicin Dosing (Induction Only):** Daunorubicin will be given at a dose of 60 mg/m^2 daily as an IV in combination with cytarabine and glasdegib or placebo, on Days 1-3. Induction chemotherapy may be repeated for one additional induction if an unsatisfactory clinical response is observed and there are no signs of cardiac toxicity. If a second induction is needed, Investigators may choose either daunorubicin 60 mg/m^2 IV on Days 1-2 or daunorubicin 60 mg/m^2 IV on Days 1-3 with cytarabine and glasdegib or placebo. If clinical signs of cardiac dysfunction are observed, a repeat MUGA/ECHO should be performed, and must demonstrate a LVEF ≥45% to receive a second course of induction chemotherapy. If a second induction therapy is required, dose must be recalculated if the weight changes by >10%.

16. **Cytarabine Dosing:** Separate cytarabine dosing and schedules will be used for Induction and Consolidation and administered using local package inserts (or SPC) or Investigational Product Manual. Alternative single-agent cytarabine consolidation schedules may be used per local prescribing information.

**Induction:** Cytarabine will be administered (in parallel to daunorubicin) at a dose of 100 mg/m^2 daily by continuous IV infusion for 7 days on Days 1-7 of induction 1. For the second induction therapy, Investigators may choose either cytarabine 100 mg/m^2 IV on Days 1-5 or on Days 1-7. Dose must be recalculated if the weight changes by >10%.

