### Induction for Intensive Chemotherapy Study

Subjects will participate in their first induction therapy for a total of 28 days. However, if a subject requires a second Induction therapy due to residual leukemia or investigator opinion, this second course may start as soon as possible following Induction 1 bone marrow evaluation.

If the induction cycle(s) extends longer than 28 days, dosing with glasdegib or placebo should continue daily in the absence of glasdegib-related toxicity that would prevent dosing.

The second induction may be delayed up to an additional 28 days from Day 28 of the first induction to allow for the subject to recover from any severe reversible hematologic or non-hematologic drug related toxicity. Treatment with glasdegib or placebo should continue during any delay before the start of the second induction in the absence of glasdegib-related toxicity that would prevent dosing. The second induction should not be performed if the subject has clinically significant cardiotoxicity (LVEF <45%) and the subject should be discontinued from treatment.

Bone marrow may be repeated at Investigator discretion as required for clinical staging any time prior to next Induction chemotherapy.

The following rules apply for progression from induction to consolidation ([Table 7](#)):

- a. Subjects who successfully obtain a <5% bone marrow blasts after induction are eligible to enter the consolidation phase of the trial 28-days from the start of the last induction. These subjects may also proceed to a second Induction per investigator judgment;
- b. Subjects with residual leukemia at the end of induction 1 may be treated with a second induction therapy;
- c. If after the second induction, the subject still shows residual or resistant leukemia, they must be discontinued from treatment and followed as described in [Section 5.5.2](#). Subjects with resistant leukemia after the first or second course of induction will be discontinued from treatment and followed as described in [Section 5.5.2](#).

Precise timings for the post first induction bone marrow assessment and remission assessment will depend on investigator judgement. In general:

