#### **5.5.2. End-of-Treatment Follow-up**

After discontinuation of study treatment (all arms), post-treatment survival status, response assessments (for those in remission), and hematologic relapse/disease progression will be collected as described in [Table 1](#) and [Table 2](#) for subjects receiving Intensive Chemotherapy and in [Table 3](#) and [Table 4](#) for subjects receiving Non-Intensive Chemotherapy until death or until termination of the study by the Sponsor.

Post treatment follow up visits will occur for the first 2 years. Subjects will return to the site for visits every 3 months starting from the last dose of study medication, for the first 2 years only.

A post treatment long-term follow-up will be completed  $\geq 3$  years starting from the last post treatment follow up visit. A telephone log will include the date of contact and survival data (including date and cause of death) and where possible, subsequent anticancer therapies, including HSCT.

The study will be considered complete once all subjects have been followed for survival for up to 5 years from the first dose of the last subject enrolled in the study, or until death, or consent withdrawal.

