### **5.5.4. Treatment Discontinuation**

If a subject demonstrates unequivocal clinically significant disease progression or unacceptable toxicity, they must be discontinued from treatment and followed as described in [Section 6.4](#).

If glasdegib/placebo is permanently discontinued for reasons other than treatment failure, hematologic relapse, objective disease progression, subject refusal, or consent withdrawal, single-agent treatment with azacitidine, or combination daunorubicin and cytarabine may be continued if, in the Investigator's judgment, a clinical benefit has been observed and following discussion between the Investigator and Sponsor.

In cases of unacceptable toxicity or pregnancy, the subject must be withdrawn from study drug combination and entered into the follow-up phase of the study.

When study treatment with both drugs of the study combination (glasdegib/placebo and azacitidine, or cytarabine and daunorubicin) is permanently discontinued, subjects will enter into the follow-up phase.

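### Protocol 7.1.1 removes subjects with LVEF below 45% before a second induction from the trial; 5.5.1.2 only stops their treatment, and the general rules keep them in survival follow-up

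*Protocol*

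**What the plan says.** One trigger, LVEF below 45% on a repeat scan before Induction 2 of the intensive study, is handled in three places.

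- **Protocol 7.1.1 (Cardiac Testing):** "the subject is not eligible to receive additional induction chemotherapy and will be removed from the trial".
- **Protocol 5.5.1.2 (Induction for Intensive Chemotherapy Study):** the second induction is not given for clinically significant cardiotoxicity, which is identified by the same 45% limit, "and the subject should be discontinued from treatment".
- **Protocol Table 1, footnote 15:** if there are clinical signs of cardiac dysfunction, the repeat scan "must demonstrate a LVEF ≥45% to receive a second course of induction chemotherapy". Nothing is said about leaving the study.

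The general rules on stopping treatment are these.

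- **5.5.2:** "After discontinuation of study treatment (all arms), post-treatment survival status, response assessments (for those in remission), and hematologic relapse/disease progression will be collected".
- **5.5.4,** for unacceptable toxicity: "the subject must be withdrawn from study drug combination and entered into the follow-up phase of the study".
- **6.2:** subjects who permanently stop both study drugs "for any reason (except death, or withdrawal of subject consent for follow-up) will enter into the follow-up phase of the study".
- **6.4:** "Subjects will be followed for survival for up to 5 years from the first visit of the last subject randomized in the study". The only earlier end points named there are the subject's death and withdrawn consent.
- **6.5** keeps two lists. Unacceptable toxicity is a reason to withdraw from treatment. The list for withdrawal from follow-up names sponsor termination, loss to follow-up, withdrawal of consent and death.

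**The concern.** The protocol treats stopping treatment and leaving the study as different acts, and 7.1.1 uses the words for the second where 5.5.1.2 uses the words for the first. Section 7.1.1 is phrased as mandatory, and it is where a site would look when a low LVEF result comes back.

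The primary analysis is overall survival in all randomised subjects, with living subjects censored at last contact (Protocol 9.2.1 and 9.3.1). A literal reading of 7.1.1 would therefore end collection of the primary endpoint in someone who has not withdrawn consent. The affected subjects both needed a second induction and developed cardiac dysfunction, so the censoring could be related to prognosis. It is also avoidable.

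**Working it through.** **1. Is it the same trigger?** Yes. Section 7.1.1 refers to a second MUGA or ECHO below 45% when a second induction is indicated. Section 5.5.1.2 adds the term clinically significant cardiotoxicity but ties it to the same limit. Both are current text, not the amendment log.

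**2. Which consequence fits the rest of the protocol?**

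| Place | Event | Consequence |
|---|---|---|
| 7.1.1 | LVEF below 45% | Out of the trial |
| 5.5.1.2 | LVEF below 45% | Off treatment |
| 5.5.1.2, rule (c) | Residual or resistant leukaemia after induction | Off treatment, followed per 5.5.2 |
| 5.5.4 | Unacceptable toxicity | Off study drugs, into follow-up |
| 6.2 | Permanent stop of study drugs, any reason | Follow-up, except after death or withdrawn consent for it |
| 7.1.2 | Confirmed pregnancy | Off treatment, into follow-up |

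Section 7.1.1 is the only outlier. The next subsection, 7.1.2, has the right wording for another safety stop.

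**3. Where would such a case show?** SAP 6.1 lists three censoring reasons for OS: alive, withdrawal of consent, lost to follow-up. Removal under the protocol is not one of them. SAP 6.5.2.1 does summarise discontinuation of treatment, of post-treatment follow-up and of study separately by reason, with study discontinuation on the full analysis set. A premature removal should appear there.

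**4. How large could it be?** The documents give no rate. A case needs entry LVEF of at least 50%, an indication for a second induction, a scan repeated because it is clinically indicated, and a result below 45%.

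The plan's own figures reproduce:

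- Fixed-design events = 4 × (1.960 + 1.282)² / (ln 0.67)² ≈ 262.1, rounded up to 263, against the stated 267 for a three-look design.
- Timeline: exponential OS with medians 21 and 31.5 months, 1:1 allocation, a linear 10-month ramp to 18 per month, 400 subjects and no drop-out give 267 deaths at 57.5 months (protocol: 58). Deaths then accrue at about 3.5 per month.

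Per missed death:

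- Share of events: 1/267 = 0.37%.
- Delay to the trigger: 1/3.5 ≈ 0.29 months.

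Illustration with assumed rates that have no source in the documents: 15–35% need a second induction, and 2–5% of those have LVEF below 45%.

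- Subjects: 400 × 0.15 × 0.02 = 1.2, up to 400 × 0.35 × 0.05 = 7.0.
- Deaths, at the design fraction 267/400 ≈ 0.67: 0.8 to 4.7.
- Delay: about 0.2 to 1.4 months.

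These subjects may fare worse than the design average, so the death counts are not strict upper limits. In the other direction, recovered death dates would lower the number missed.

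**The case against.** The strongest reply is that the protocol already settles the matter. Section 6.2 covers any reason with only two exceptions, 5.5.2 and 5.5.4 agree, and 5.5.1.2, which governs the treatment decision, has suitable wording. The words study and trial are also used loosely elsewhere: 5.5.1.2 describes remaining on study for one to four consolidation courses, and the heading of 8.1.3 speaks of withdrawal from the study for adverse events. This stands as evidence of intent. It does not make the sentence harmless. Section 7.1.1 is specific and mandatory, no clause says which text prevails, and the follow-up list in 6.5 is introduced with may include, so it does not strictly shut out other reasons.

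Mitigation also counts. Section 6.4 adds: "Public records may be used for contact information and/or to document date of death, as permitted by local law". Section 6.5, in its paragraph on missed visits, asks for every effort to document outcome. Both reduce the loss without guaranteeing recovery.

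A reader might infer three stronger things that the documents do not support.

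- **That power is lost.** With 4.7 deaths missing and not replaced, a fixed-sample approximation at the final boundary of 0.023 gives 89.4% against 89.9%. But Protocol 9.3.1 sets the primary analysis at about 267 deaths, and the SAP introduction sets the cutoff by the number of OS events. Missed deaths are replaced by waiting.
- **That the cases would be hidden.** They would not form a separate OS censoring reason, but the disposition tables should show them.
- **That one arm is favoured.** Nothing in the documents shows a difference between arms in how often this would occur.

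**Conclusion.** There is a real inconsistency between 7.1.1 and both 5.5.1.2 and 6.2. The intended reading is follow-up. The residual risk is that a site takes 7.1.1 at its word and OS is censored, possibly informatively, in a very few randomised intensive-study subjects.

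Confidence is high on the wording conflict. The consequence for OS depends on three things that the documents do not establish: that the trigger occurs, that a site reads 7.1.1 literally, and that no death date is later found. The size is a slight delay in reaching the event count, about 0.3 months per missed death under the protocol's accrual and survival assumptions. The 267 deaths, 400 subjects and 90% power are unaffected. Severity: minor.

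**What to change.** In Protocol 7.1.1, replace the words on removal from the trial with: *will be discontinued from study treatment and will enter post-treatment and survival follow-up (Section 6.4) unless consent for follow-up is withdrawn*.

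The cost is one sentence in a clarification letter or the next amendment. It adds no visits beyond the follow-up already planned, and the SAP needs no change.
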